We specifically note that this is a suitable treatment modality for all physicians, both osteopathic and allopathic, as we merge our skill sets over time in a unified manner. As mentioned, the training of a physician usually dictates the management decisions regarding MTP treatment. This study was conducted in a post graduate training institution that has multiple specialty programs with osteopathic recognition. In the single accreditation system, collaborating with allopathic physicians and exposing allopathic residents to osteopathic treatment options was viewed an advancement for patient centered care and osteopathic awareness. As more allopathic physicians expand their skill sets and complete OMT courses, demonstrating the efficacy of a common treatment modality compared to OMT will assist with treatment choice. Comparable efficacy of both options will help patients choose the option that best meets their needs and physicians choose the option that best augments their skill set.

Being a pilot study, we anticipated a considerable degree of limitations throughout the study. Limitations include but are not limited to low sample size, majority female participants, and substantial difference in mean age between the two groups. Additionally, the OMT intervention group had a significantly lower mean pre-intervention pain level compared to the lidocaine group which made it difficult to do a true comparative analysis between groups. However, as a pilot study, demonstration of OMT non-inferiority compared to a standard treatment modality, creates a stepping stone for future research to investigate the comparative efficacy of OMT on a larger scale and we therefore anticipate future trials with larger number of participants to demonstrate more significant data and results.

Conclusion

Based on our study, OMT has comparable value with lidocaine injection technique as a treatment modality for active TrPs in the upper trapezius region. Both techniques demonstrate considerable decrease in pain intensity from baseline and thus it allows for increased collaboration between osteopathic and allopathic practitioners to promote patient centered care.

References

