On the other hand, there has been fewer research investigating the effects of manual treatment on trigger points. Travell and Simons initially treated trigger points with ischemic compression but later changed their recommendation to applying gentle digital pressure to trigger points ¹⁶. A recent study done on traction-compression-stretch technique compared with ischemic compression showed some, albeit minor, increased outcome measures (pain pressure threshold) warranting clinical investigation ⁶. (We can use their comparative model and statistics since it would be similar to our concept) Another study compared active release and muscle energy techniques in treating latent trigger points of the upper trapezius and found that both techniques were equally effective in increasing cervical range of motion and decreasing pain and upper trapezius thickness⁷. Other studies have also shown interest in similar osteopathic manipulative techniques such as counterstrain, myofascial release, facilitated positional release and high velocity-low amplitude thrust techniques in treating trigger points^{3,16-18}.

Studies have showed that the upper trapezius is one of the most common muscles affected by myofascial pain syndrome ^{19,20} leading to referred pain manifesting as headaches and stiff neck.

There is no consensus as to which treatment method is superior, with the decision to treat in a certain way/technique largely based upon the training received by the individual physician rather than the characteristics of the trigger point itself. There are currently no studies evaluating the efficacy of the various treatment options specifically osteopathic manipulative treatment vs. trigger point injections. Thus, the intention of the present study was to determine the efficacy rates of muscle energy techniques vs. dry needling in treating MTPs in the upper trapezius region.

Study Objective

The primary aim of this study is to observe whether osteopathic manipulative treatment or traditional lidocaine/dry needling technique is more efficacious or non-inferior and similar in treating myofascial trigger points in the upper trapezius region as it relates to quality of life and improvement in pain scores.

Study Design

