The outcome measures, reported pain and quality of life, will be analyzed separately using univariate analyses. The differences between the treatment groups across time periods will be analyzed. A two-factor analysis of variance (ANOVA) will be performed for each dependent variable to determine the

difference between treatment groups at the different time points (before the intervention, immediately after the intervention, and a week post the intervention). A 2 x 3 mixed factor design will be used in order to evaluate the between subjects data (intervention type) across the repeated measures (three time periods).

Study Administration

The primary records of data will be in form of pre- and post- intervention surveys. Each survey will contain a random code to link the patient to the survey data and that list will be kept separate from the surveys. All physical copies of data will be stored primarily at [name] office under lock and key with key access only to them. Data collected through Atlanticare pain clinic will be maintained through one set of copies which will be stored at [name] office under lock and key with key access only to them. Data collected through PCOM will be maintained through one set of copies which will be stored at [name] office under lock and key with key access only to them. Surveys administered through email will be sent through a secure link and all online data will be encrypted with access only to principal investigators and research personal. All data obtained through email will be stored on the principal investigator's computer which is password protected. All data and records generated during this study will be kept confidential in accordance with Institutional policies and HIPAA on subject privacy and the investigator and other site personnel will not use the data and records for any purpose other than conducting the study. The identifiers and other data will be destroyed 5 years after study completion in compliance with the Atlanticare Regional Medical Center data retention policy.

References

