Participants presenting to the Atlanticare Pain Management clinic received a lidocaine injection after dry needling into the location of the MTP by a board-certified pain management physician. First, the upper trapezius MTP was identified and isolated. After application of a coolant to numb the area, the isolated trigger point was penetrated using a 30-gauge needle, to a depth adjusted depending on the patient, into the subcutaneous tissue. The duration of treatment was approximately 1-2 minutes. Once the myofascial tension was relieved, 2 mL of 0.5% lidocaine was injected into the MTP.

After their respective interventions, the patient completed an immediate post-intervention survey, consisting of a 0-10 pain scale. Finally, approximately 7-10 days after the intervention, patients were contacted by telephone to complete the one-week post-intervention survey consisting of a 0-10 pain scale.

Outcome Measures

Pain intensity; measured using a point system; where 0 = no pain and 10 = maximum pain. Although this is a subjective measurement by the patient, we are interested in looking at the difference between pre- and post-intervention pain intensity ratings.

Data Analysis

The data was analyzed using R software. Values of interest include mean, median, standard deviation, normal distribution, confidence intervals etc. Intergroup and intra-group comparisons were conducted using independent t-tests and paired t-tests, respectively. Alpha level is set at 0.05 and p values less than that will be considered statistically significant. A descriptive analysis of the outcome variables was conducted to compare between the intervention groups. The homogeneity of sociodemographic data (age, sex, comorbid conditions) and outcome measures were analyzed using the Fischer test and Pearson chi square test, respectively.

The outcome measures were analyzed separately in both treatment groups. The contrast between the treatment groups was analyzed. A univariate analysis of the difference of the outcome variables at the different time points (before the intervention, immediately after the intervention, and a week post the intervention) were obtained through the student *t*-tests. A multivariate analysis was carried out using multiple logistic regression models with age, sex, and intervention group (Injection = 0, OMM = 1) factored as the independent variables.

Results

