The study was completed at two primary locations. There were a total of 10 eligible participants from the lidocaine treatment group and 21 eligible participants from the OMM treatment group enrolled after screening for the inclusion and exclusion criteria. 1 subject from the lidocaine treatment group was lost during follow-up at one week post intervention and thus excluded from the per protocol analysis of the study. The remaining participants' data were analyzed in SPSS 26. No significant difference was found between the two groups in regard to sociodemographic data (Table 1). At baseline, the OMM group had a mean pain intensity level of 2.76 (SD 1.8) while the lidocaine treatment group had a mean pain intensity level of 7 (SD 2.8). Descriptive statistics of pain intensity between the two groups demonstrate considerable variance (Table 2).

Within the OMM group, an independent samples t-test found a statistically significant difference between the pre-intervention and immediate post-intervention pain levels, $t(20) = 2.10, p = .048$. The mean pre-intervention pain level ($M = 2.76, SD = 1.84$) was significantly higher than the immediate post intervention pain level ($M = 1.86, SD = 0.96$). An independent samples t-test found a statistically significant difference between pre-intervention and one-week post-intervention pain levels, $t(20) = 2.68 p = .014$. The mean pre-intervention level of pain ($M = 2.76, SD = 1.84$) was significantly higher than one-week post-intervention ($M = 1.81, SD = 2.01$).

Within the lidocaine group, an independent samples t-test did not demonstrate a statistically significant difference between pre-intervention and immediate post-intervention pain levels, $t(20) = 1.17, p = 0.27$. The mean pain level pre-intervention ($M = 7, SD = 2.87$) was higher than immediately post-intervention ($M = 6.60, SD = 2.32$). When evaluating the difference in level of pain from pre-intervention to one-week post-intervention, an independent samples t-test was not statistically significant, $t(20) = 2.16 p = .062$. The mean level of pain pre-intervention ($M = 7, SD = 2.87$) was higher than one-week post-intervention ($M = 4, SD = 2.18$). Pain intensity between the two groups are also demonstrated graphically in Figure 1, with time point one corresponding to pre-intervention, two corresponding to immediately post-intervention and three corresponding to 1 week post intervention.

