To investigate the treatment effect between groups across time, a mixed design two factor ANOVA was utilized. As expected, due to small sample size, heterogeneity of covariance matrices was detected. This is considered a limitation of the study. Also, since a repeated measures design was implemented across three time periods, Mauchly's test of sphericity was examined and found to be significant ($p = .042$). This indicates that sphericity cannot be assumed, so a Greenhouse-Geisser statistic was computed. A statistically significant interaction effect was detected, $F(1.65, 56) = 3.90, p = .034$. Due to p-value being less than 0.05, we can confidently reject the null hypothesis and accept the alternative hypothesis.

[figure not shown]
Table 1.

Sociodemographic Data	Mean (SD) or Number (%)		P value
	OMM (n = 21)	Lidocaine (n = 10)	
Sex (%), n = 31 (100%)	21 (100)	10 (100)	
Male, n = 7 (22.6%)	5 (23.8)	2 (20)	
Female, n = 24 (77.4%)	16 (76.2)	8 (80)	
Age, y			
Subjects from 20 – 29 y, n = 22 (71%)	21 (100)	1 (10)	
Subjects from 30 – 39 y, n = 1 (3.2%)	0	1 (10)	
Subjects > 60y, n = 8 (25.8%)	0	8 (80)	
Ethnicity			
Caucasian, n = 20 (64.5%)	11 (52.4)	9 (90)	
African American, n = 1 (3.2%)	1 (4.8)	0	
Latino or Hispanic, n = 4 (12.9%)	3 (14.3)	1 (10)	
Asian, n = 6 (19.4%)	6 (28.6)	0	
Pain Intensity			
Pre-intervention	2.76 (1.8)	7 (2.8)	
Post-intervention (immediate)	1.86 (0.9)	6.6 (2.3)	0.026
Post-intervention (one week)	1.81 (2.0)	4 (2.2)	0.062

Table 2.

	Group	Mean	Std. Deviation	N
Pre-intervention Pain	OMM	2.76	1.84	21
	Lidocaine	7.00	3.04	9
	Total	4.03	2.96	30
Post-intervention immediate pain	OMM	1.86	0.96	21
	Lidocaine	6.56	2.45	9
	Total	3.27	2.66	30
Post-intervention 1 week pain	OMM	1.81	2.01	21
	Lidocaine	4.00	2.17	9
	Total	2.47	2.27	30

Figure 1.

Discussion

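### Equal efficacy and non-inferiority are claimed without a margin or a between-group estimate with a confidence interval, after an interaction test that rejected equal time courses

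*SAP*

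**What the plan says.** **Aim.** The protocol's Study Objective asks whether one treatment is "more efficacious or non-inferior and similar in treating myofascial trigger points in the upper trapezius region". No margin appears there or anywhere in the SAP.

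**Planned between-group test.** The protocol's Data Analysis specifies a two-factor mixed ANOVA, treatment group by three time points. SAP Data Analysis does not list it, but SAP Results reports it.

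**SAP methods.** The stated tests are: "Intergroup and intra-group comparisons were conducted using independent t-tests and paired t-tests, respectively". Outcome Measures says "we are interested in looking at the difference between pre- and post-intervention pain intensity ratings", which points to change. Data Analysis adds "A univariate analysis of the difference of the outcome variables at the different time points" by t-tests and "multiple logistic regression models with age, sex, and intervention group (Injection = 0, OMM = 1) factored as the independent variables". Confidence intervals are listed as values of interest. No primary time point is named.

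**SAP results.** The interaction is F(1.65, 56) = 3.90, p = .034, followed by: "Due to p-value being less than 0.05, we can confidently reject the null hypothesis and accept the alternative hypothesis". No between-group difference with an interval is given. On demographics the text says: "No significant difference was found between the two groups in regard to sociodemographic data (Table 1").

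**SAP Discussion.** It says neither technique was clearly superior, that the reduction was larger with OMM immediately and with lidocaine at one week, that efficacy was equal, and that non-inferiority was demonstrated. It also concedes that the baseline pain gap made a true comparison difficult and that mean age differed substantially.

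**The concern.** A claim of non-inferiority needs a margin and a confidence bound to set against it. A claim of equal efficacy needs limits on both sides. The documents supply none of these. What they do supply is a test that rejected the hypothesis of parallel time courses, which cannot serve as evidence of equality.

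The groups were also not comparable at entry: clinic determined treatment, baseline pain differed by more than 4 points, and ages hardly overlapped. The Discussion offers the equal-efficacy conclusion as a basis for patients and physicians to choose between treatments, so the claim has consequences.

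**Working it through.** **1. Reproduce the printed tests.**
- Interaction: F = 3.90 on (1.65, 28 × 1.65 = 46.2) df gives p = 0.0345, consistent with .034.
- OMM within-group: t = 2.10 and 2.68 on 20 df give p = 0.049 and 0.014, against .048 and .014 printed.
- Lidocaine within-group: t = 1.17 gives p = 0.272 on 9 df (0.256 on 20), and t = 2.16 gives 0.063 on 8 df (0.043 on 20). The printed p values (0.27 and .062) fit 9 and 8 df, not the printed 20.
- Results calls these independent-samples tests. Independent tests on the OMM means and SDs would give t = 1.99 and 1.60, so the printed values are taken as paired.

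**2. SD of change** = |mean change| × √n / paired t.
- OMM immediate: 0.90 × √21 / 2.10 = 1.96
- Lidocaine immediate (n = 10): 0.40 × √10 / 1.17 = 1.08
- OMM one week: 0.95 × √21 / 2.68 = 1.62
- Lidocaine one week (n = 9): 3.00 × √9 / 2.16 = 4.17

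**3. OMM minus lidocaine; negative favours OMM.** Welch SE = √(s₁²/n₁ + s₂²/n₂).
- One-week change: -0.95 - (-3.00) = +2.05. SE = √(1.62²/21 + 4.17²/9) = 1.43 on 9.1 df; 95% CI 2.05 ± 2.26 × 1.43 = -1.19 to 5.29, p = 0.19. Student: SE 1.04 on 28 df, -0.09 to 4.19, p = 0.059.
- Immediate change (21 v 10): -0.90 - (-0.40) = -0.50. SE = √(1.96²/21 + 1.08²/10) = 0.55 on 28.2 df; 95% CI -1.62 to 0.62, p = 0.37.
- Immediate change, completers only (21 v 9): -0.46, Welch -1.64 to 0.72. The patient later lost contributed a change of 0 (totals 70 - 63 = 7 before, 66 - 59 = 7 after), which makes the completer SD 1.14.
- Raw pain at one week: 1.81 - 4.00 = -2.19, Welch -4.00 to -0.38. The sign is opposite to that for change because baseline differs by 2.76 - 7.00 = -4.24.

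**4. Baseline-adjusted sensitivity at one week.** A common-slope model gives -1.17 (-3.38 to 1.05). The implied slopes are 0.71 (OMM) and -0.18 (lidocaine), F(1, 26) = 8.9, p = 0.006, so the common slope is not credible and the baselines overlap poorly.

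**5. What the interaction reflects.** The group differences at the three times are -4.24, -4.70 and -2.19, with mean -3.71. Interaction SS = (21 × 9 / 30) × (0.53² + 0.99² + 1.52²) = 6.3 × 3.571 = 22.50. Each step taken as a single contrast has SS = 6.3 × d²/2:
- immediate to one week, d = 2.51: 19.85 (88%)
- baseline to one week, d = 2.05: 13.24 (59%)
- baseline to immediate, d = -0.46: 0.67 (3%)

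These contrasts overlap, so the percentages do not add to 100.

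**6. Table 1.**
- Aged 20-29: 21 of 21 OMM against 1 of 10 lidocaine; Fisher exact p = 5 × 10⁻⁷.
- The one-week P value, 0.062, equals the within-lidocaine paired p in Results.
- The immediate P value, 0.026, equals the interaction p with sphericity assumed: F(2, 56) = 3.90 gives 0.026.
- Actual between-group Student tests give p < 0.001 (raw) and 0.46 (change) immediately, and 0.012 (raw) and 0.059 (change) at one week. Rounding of the inputs moves the last value only between 0.057 and 0.061, so it does not reach 0.062.

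**The case against.** The documents are not silent on scale. Outcome Measures, the mixed ANOVA and the Discussion's comparison of reductions all work on change, and an omnibus interaction test needs no primary time point to be valid as a test. The Discussion calls the study a pilot, discloses the age and baseline imbalance, and says neither technique was clearly superior. Results discloses heterogeneous covariance matrices. All of this stands. It makes the open scale and time point secondary, but it supplies no margin, estimate or interval.

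Three stronger readings are tempting and should be resisted:
- *The raw-versus-change reversal overturns a reported result.* The SAP text draws no conclusion from raw post-treatment pain between groups. The reversal only shows why the intergroup scale needs stating.
- *The interaction p-value says nothing about change from baseline.* The immediate-to-one-week step is the largest, but baseline to one week alone captures 59% of the interaction SS.
- *The significant interaction shows that lidocaine is better at one week.* Both the Welch and the Student interval for that change include zero, and clinic, age and baseline pain cannot be separated from treatment.

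**Conclusion.** The point holds and should be fixed. Equal efficacy and non-inferiority are not supported: there is no margin, no between-group estimate with an interval is reported, and the planned test found that the time courses differed. On change from baseline at one week, the upper limit allows lidocaine to be better by 4.2 points (Student) or 5.3 points (Welch) on a 0-10 scale.

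The change intervals rest on the printed t values being paired, on lidocaine df of 9 and 8, and on rounded inputs. The lidocaine change SD at one week comes from nine patients and is unstable. The one-week sign reversal needs only the Table 2 means. The statement that sociodemographic data did not differ is contradicted by Table 1, and neither pain P value in that table is a between-group test at its time point. Supplying estimates and intervals would not by itself rescue the claims, because the margin would still be missing and the confounding would remain.

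**What to change.** **In SAP Data Analysis:**
- List the mixed ANOVA, and say that the intergroup t-test is on change from baseline.
- Add, labelled post hoc, the between-group difference in mean change with a Welch 95% CI: immediately on all 31 patients (30 completers as a check) and at one week on the 30 completers.
- State that no primary time point or margin was set in advance.
- Show baseline-adjusted models as sensitivity only, noting the unequal slopes and poor baseline overlap.
- State the logistic model's outcome and result, or state that it was not performed. As written it has no defined binary outcome, omits baseline pain and has no reported result.

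**In Results and Table 1:** correct the sociodemographic statement and the two pain P values.

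**In the Discussion and Conclusion,** replace the equal-efficacy, non-inferiority and comparable-value wording with:

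> Mean pain fell in both groups. The time courses differed (interaction p = .034), but the between-group differences in change from baseline were imprecise, no non-inferiority margin was set, and the comparison is confounded by clinic, age and baseline pain; neither equal efficacy nor non-inferiority was shown.

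**Cost:** wording changes and a short reanalysis of data already collected. The paper loses its equivalence message. The added estimates are chosen after the results were known, and they are exposed to regression to the mean and to a floor effect: OMM could fall by at most 2.76 points on average, less than lidocaine's observed 3.00.

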Group 2 will be comprised of patients from AtlantiCare Regional Medical Center pain clinic and will be administered trigger point dry needling and lidocaine injection. The treatment will be administered by the pain clinic attending physician. After application of a coolant to numb the area, the isolated trigger point will be penetrated using a 30-gauge needle, to a depth adjusted depending on the patient, into the subcutaneous tissue. The patient will be warned about possible unpleasant sensations and mild pain associated with contraction of the tight band of muscle. Multiple needle insertions will be attempted to achieve MTrP inactivation, with the needle being withdrawn to the subcutaneous layer but not from the skin during each insertion, approximately lasting for 1-2 minutes ^{26,27}. Once the fascial tension is relieved, 0.5% lidocaine will be injected, and the needle will be withdrawn from the skin. The procedure will be terminated with hemostasis achieved.

Once the intervention is completed, the patient will be asked about the reduction in pain following the intervention and administered the post intervention survey. A week after the intervention, they will be called/mailed to ask about their pain intensity using the same post intervention survey by the medical students.

Safety Management:

Patients are free to withdraw from the study at any time should they choose to. Since the study procedures are not greater than minimal risk, adverse events are not expected. If any serious adverse effects or unaccounted events may occur, they will be reported to the IRB and patients will be discontinued from the study. The data from withdrawn patients will not contribute to the study statistics.

Data Analysis

The data will be analyzed using SPSS version 27.0 for Windows (IBM Corp. Released 2020. IBM SPSS Statistics for Windows, Version 27.0. Armonk, NY: IBM Corp). Values of interest include measures of central tendency, i.e. mean, standard deviation, normal distribution, confidence intervals etc. To be considered a statistically significant finding, the alpha level will be set at 0.05. A descriptive analyses of the outcome variables will be conducted to compare between the intervention groups. The homogeneity of sociodemographic data (age, sex, comorbid conditions) and treatment groups will be analyzed using the Fischer test and Pearson chi square test, respectively.

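### The SAP gives the 0-10 pain scores two conflicting between-group tests, and the P values printed beside those scores in Table 1 are not the between-group t-tests of the means in their rows

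*SAP*

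**What the plan says.** The SAP's Outcome Measures section lists one outcome, a pain rating "where 0 = no pain and 10 = maximum pain". Its Data Analysis section then gives two instructions for comparing the groups on it:

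- "Intergroup and intra-group comparisons were conducted using independent t-tests and paired t-tests, respectively".
- On homogeneity, sociodemographic data and "outcome measures were analyzed using the Fischer test and Pearson chi square test, respectively". Taken in order, Fisher's test goes with the demographic variables and Pearson chi-square with the outcome measures.

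The protocol's matching sentence ends differently: "and treatment groups will be analyzed using the Fischer test and Pearson chi square test, respectively". It does not assign chi-square to the pain scores.

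The threshold is "Alpha level is set at 0.05 and p values less than that will be considered statistically significant". Sidedness is not stated.

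Table 1 sets the OMM and lidocaine means side by side with a single P value column and names no test. In the pain rows it prints 0.026 (immediate) and 0.062 (one week). The baseline cell is blank. The Results text gives .062 as the lidocaine group's own change from baseline to one week. The only between-group test in that text is the group-by-time interaction from a mixed ANOVA, p = .034.

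**The concern.** Two separate faults sit close together.

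The first is the choice of test. A chi-square test treats 0 to 10 as unordered labels and needs reasonable expected counts, which a study of this size cannot supply. A reader of the SAP cannot tell which test governs the between-group comparison of scores.

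The second is the table. A P value printed beside two group means will be read as the test of those two means. If it is something else, the table misinforms. The one-week entry matters most, because 0.062 falls above the stated alpha and would be taken as no difference between groups. The SAP's Discussion goes on to claim equal efficacy and a demonstration of non-inferiority, and a value of 0.062 in a group-comparison table seems to support those claims.

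**Working it through.** **Inputs.** All are from the SAP. Enrolment was "10 eligible participants from the lidocaine treatment group and 21 eligible participants from the OMM treatment group", and "1 subject from the lidocaine treatment group was lost during follow-up at one week post intervention", so lidocaine has n = 10 or 9. From Table 2 (OMM n = 21, lidocaine n = 9), mean (SD):

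- Baseline: 2.76 (1.84) and 7.00 (3.04)
- Immediate: 1.86 (0.96) and 6.56 (2.45)
- One week: 1.81 (2.01) and 4.00 (2.17)

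For lidocaine at n = 10 the Results text gives 7.00 (2.87) and 6.60 (2.32). Tests are taken as two-sided.

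**Chi-square.** The expected count in a lidocaine cell is (patients with that score) × 9/30. For it to reach 5, at least 5 × 30/9 = 16.7, so 17 of the 30 patients, must share one score. At most one score can do that, so every other lidocaine cell is below 5. A simulation of 4,000 trials with rounded, clipped normal scores at the one-week means and SDs (the distribution is an assumption) put 96% of expected counts below 5. Power was 32% for chi-square and 64% for Welch.

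**Can the printed P values be reproduced?** The formula is t = difference / SE. The pooled form is SE = sqrt[s²(1/n1 + 1/n2)] with s² = [(n1−1)s1² + (n2−1)s2²]/(n1+n2−2). The Welch form is SE = sqrt(s1²/n1 + s2²/n2).

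One week:
- Pooled: s² = (20 × 4.0401 + 8 × 4.7089)/28 = 4.231; SE = sqrt[4.231 × (1/21 + 1/9)] = 0.820; t(28) = 2.19/0.820 = 2.67; p = .012; 95% CI 0.51 to 3.87.
- Welch: SE = sqrt(4.0401/21 + 4.7089/9) = 0.846; t = 2.59 on 14.2 df; p = .021; 95% CI 0.38 to 4.00.

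The same method for all three rows:

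| Row | Difference | Pooled p | Welch p | Printed in Table 1 |
|---|---|---|---|---|
| Baseline | 4.24 | <.001 | .003 (n=9), .001 (n=10) | blank |
| Immediate | 4.70 (n=9), 4.74 (n=10) | <.001 | <.001 | 0.026 |
| One week | 2.19 | .012 | .021 | 0.062 |

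No pain row gives 0.026 or 0.062, so a printed value shifted by one row would not explain them either.

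**Where the printed values may come from (inferred).**
- 0.062: the lidocaine within-group test has t = 2.16. On 8 df this gives p = .063 (.0623 to .0633 over rounding of t), in line with the reported .062. On the 20 df printed in the text it would give .043.
- 0.026: the interaction F = 3.90 has a tail area of .0260 on (2, 56) df, that is, without the sphericity correction. With the correction (1.65 and 1.65 × 28 = 46.2 df) it is .034, the value reported.

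**Change from baseline.** The within-group t values behave as paired tests (20 df for 21 patients), so the SD of change is mean change × sqrt(n)/t.
- OMM: mean fall 0.952 (20/21, taking whole-number scores); SD = 0.952 × sqrt(21)/2.68 = 1.63.
- Lidocaine: mean fall 3.00; SD = 3.00 × 3/2.16 = 4.17.
- Difference in change at one week: −3.00 − (−0.95) = −2.05. Pooled p = .060, 95% CI −4.18 to 0.09. Welch p = .19, 95% CI −5.29 to 1.19.
- Immediate: difference in change about 0.5 the other way, p = .37 to .52.

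**Approximate baseline adjustment at one week.** The common slope implied by these SDs is 0.24, so the adjusted difference is 2.19 − 0.24 × 4.24 = 1.17, 95% CI −1.05 to 3.39, p = .29. The implied baseline to one-week correlations differ in sign (0.65 OMM, −0.26 lidocaine), so a common slope is itself doubtful.

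**The case against.** The SAP does name a suitable between-group test in the same paragraph. Chi-square appears only in a sentence about homogeneity, and the protocol's version of that sentence refers to treatment groups, which suggests a faulty edit. The Results name only t-tests and a mixed ANOVA, so nothing shows that chi-square was ever run on the scores. This stands. It makes the first fault a conflict in wording, not evidence of a wrongly analysed outcome.

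It may also be said that the P values are not meaningless. The value 0.026 coincides with the uncorrected interaction test, which does contrast the groups over time. The pooled test of one-week change (.059 to .060 over rounding) comes near 0.062. A chi-square p cannot be checked without individual data. This too stands, and it rules out saying that the values match no between-group analysis at all. It does not rescue the table: an interaction over three time points is not the immediate comparison, the change-score value does not equal 0.062, and no test is labelled.

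A reader might infer that Table 1 conceals a real one-week treatment difference. The documents do not support that. Both means are printed, the gap narrows from 4.24 to 2.19, and the larger fall is in the lidocaine group without reaching significance. The Discussion also states openly that the lower OMM baseline made a true comparison difficult. The p<.001 in the immediate row likewise reflects a gap already present at baseline.

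**Conclusion.** Wrong as written, in two limited respects. The SAP assigns two conflicting tests to the pain scores, one of them unsuitable for an ordered 0-10 scale at this sample size. Table 1's P values are not the between-group t-tests of the means they accompany: 0.026 is printed where the t-test gives p<.001, 0.062 where it gives .012 or .021, and nothing where baseline gives .003 or less. Only the one-week entry changes sides of the 0.05 threshold.

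Neither reading of the one-week row bears on efficacy. The score difference of 2.19 follows a larger baseline gap and is not a treatment effect. The printed 0.062 is no support for equal efficacy or non-inferiority.

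The recomputation rests on the printed means and SDs, two-sided tests, and n = 9 or 10 for lidocaine; the conclusion is the same for either n. The change-score and adjusted results also rest on SDs recovered from the reported t values. The origins of 0.026 and 0.062 are inferred, not documented.

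**What to change.** - In the SAP's Data Analysis section, delete chi-square for the pain scores. Keep the independent t-test in Welch form, with the mean difference and 95% CI. Keep Fisher's exact test for categorical sociodemographic data, and reconcile the sentence with the protocol's.
- In Table 1, replace the P entries for all three pain rows with between-group results that name the test and the lidocaine n (9 or 10), or delete the column. By Welch at n = 9 the values are .003 at baseline, <.001 immediately and .021 at one week. Add a note that these describe scores and are not treatment effects.
- Base any treatment claim on a baseline-adjusted comparison with its CI, fitted to the individual data. Say that it will be imprecise: the approximate one-week interval above runs from −1.05 to 3.39, and the groups start 4.24 points apart.

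The cost is a sentence of SAP wording, one table column and a short reanalysis of data already held.
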